6.2.2. Confirmed IC-OR

Analysis set: Participants with CNS metastases based on Investigator Assessment

Analysis methodology:

The IC-OR will be summarized similar to OR (as described above in section 6.2.1), in Safety Population with CNS metastases based on investigator assessment. Surgery or radiotherapy of extracranial lesions will not affect the determination of IC-OR.

6.2.3. DoR

Analysis set: Subset of Participants with confirmed objective response

Analysis methodology:

DoR will be calculated on every participant showing OR as follows:

DoR (months) = [first date of PD or death/censoring – first date of CR/PR subsequently confirmed+1]/30.4375

DoR data will be censored as follows:

- For participants who start a new anticancer therapy prior to an event, censoring will be at the last adequate tumor assessment (see Section 5.2.9) prior to the start of new anticancer therapy. Note: if date of progression occurs on the same date as the start of new anticancer therapy, the progression will be counted as an event.
- For participants with documented progression or death after two or more missing tumor assessments, censoring will occur at the last adequate tumor assessment prior to the missing assessments. In this study antitumor activity will be assessed through radiological tumor assessments conducted at screening and every 12 weeks until disease progression regardless of initiation of subsequent anticancer therapy. The allowable time window for disease assessments is ±1week while on treatment and whenever disease progression is suspected (eg, symptomatic deterioration). Therefore time without adequate assessment is defined as 24 weeks plus 2 weeks.
- All other participants alive without objective progression will be censored on the date of the last adequate tumor assessment.

The date of tumor response at each nominal timepoint based on the investigator assessments will be used for determining the dates of last adequate assessment for censoring purposes.

The censoring and event date options to be considered for the DoR analysis are presented in Table 2.

Table 2. Outcome and event dates for DoR analyses

Scenario	Date of event/censoring	Outcome
Progression or death ≤ 26	Date of progression or death	Event
weeks after last adequate		
tumor assessment		
Progression or death > 26	Date of last adequate	Censored
weeks after the last adequate	assessment documenting no	
tumor assessment	PD prior to anticancer	
No progression	therapy or missed	
New anticancer therapy	assessments	
given prior to PD		

Intercurrent events and missing data: data on response after subsequent anticancer therapy is administered will be excluded.

Summaries used for reporting: Kaplan-Meier estimates (product-limit estimates) will be presented together with a summary of associated statistics including the median DoR time with two-sided 95% CIs. The CIs for the median will be calculated according to Brookmeyer and Crowley.

When the number of participants with PD after a confirmed CR or PR is small, the use of Kaplan-Meier method is limited due to high number of censored observation, so the DoR will be summarized using number (%) of participants with events and of participants censored with DoR in the following categories: less than 6 months, $\geq 6 - \langle 9 \rangle \geq 9 - \langle 12 \rangle \geq 12 - \langle 15 \rangle \geq 15 - \langle 18 \rangle \geq 18 - \langle 21 \rangle \geq 21 - \langle 24 \rangle$, and ≥ 24 months.

Frequency (number and percentage) of participants with each event type (PD or death) and censoring reasons will be presented along with the overall event and censor rates.

Reasons for censoring will be summarized according to the categories in Table 3. If a participant meets multiple definitions for censoring the list will be used to define the hierarchy.

Table 3. Censoring Reasons and Hierarchy for DoR analyses

Hierarchy	Condition	Censoring Reason
1	Event more than 26 weeks from last adequate post-baseline tumor assessment/start date	Event after missing assessments ^a
2	No event and [withdrawal of consent date ≥ start date OR End of study (EOS) = Subject refused further follow-up]	Withdrawal of consent
3	No event and lost to follow-up in any disposition page	Lost to follow-up
4	No event and none of the conditions in the prior hierarchy are met	Ongoing without an event

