## 7. ASSESSMENTS

## 7.1. Antitumor Activity Assessments

Tumor assessments will include all known or suspected disease sites. Computed tomography (CT) or magnetic resonance imaging (MRI) scans of chest abdomen pelvis (CAP) and MRI of the brain will be performed at Screening. Gadolinium contrast enhanced MRI must be used for assessment of CNS lesions with contingent slices of 1 mm for lesions 5 mm to 10 mm in size, 5 mm for lesions greater than 10 mm. For all tumor assessments, the method of assessment that was used at Screening should be the same method used throughout the study. CT and MRI scans to be done at every 12 weeks  $\pm 1$  week till the end of treatment. Tumor assessment should be repeated at the end of treatment if more than 6 weeks have passed since the last evaluation. Moreover, radiological tumor assessments will be conducted whenever disease progression is suspected (eg, symptomatic deterioration).

Assessment of response will be made using RECIST version 1.1 (Appendix 3). Confirmation of response will be required at least 4 weeks after initial response is observed.

All participants' files and radiologic images must be available for source verification.

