5.2.3. Definition of Start of New Anticancer therapy

Start date of new anticancer therapy (drug, radiation, surgery) is used for definition of ontreatment in safety analyses (see Section 3.5.1) and for censoring in antitumor activity analyses (see Section 6.2.3).

The start date of new anticancer therapy is the earliest date after first dose of Lorlatinib amongst the following:

• Start date of anticancer drug therapy recorded in the 'Concomitant Medications' CRF pages with 'Category of medication' = 'Follow-up Cancer Therapy'

- Start date of radiation therapy recorded in 'Radiation Treatment' CRF page with 'Subcategory' = 'Curative in intent'
- Surgery date recorded in 'Non-drug Treatments' CRF pages with 'Category' = 'Cancer Surgery' and 'Outcome of Procedure' = 'Resected' or 'Partially Resected'.

When start date of anticancer therapy is missing or partially missing, the imputation rules described in Section 5.3.2.4 should be applied using 'Concomitant Medications', 'Radiation Treatment', and 'Non-drug Treatments' CRF pages.

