6.2.4. IC-DoR

Analysis set: Subset of Safety Participants with confirmed Intracranial objective response

Analysis methodology: IC-DoR (months) = [first date of PD in brain lesions or death/censoring – first date of IC-OR (CR/PR subsequently confirmed)+1]/30.4375

For participants whose IC-OR proceeds from PR to CR, the onset of PR is taken as the onset of response.

Censoring for IC-DoR will be identical to the censoring rules presented above for DoR.

Intercurrent events and missing data: data on response after subsequent anticancer therapy is administered will be excluded.

Summaries used for reporting: The IC-DoR will be summarized similar to DoR (as described above in section 6.2.3), in Participants with CNS metastases. Surgery or radiotherapy of extracranial lesions will not affect the determination of IC-DoR.

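### SAP Table 3 has no censoring reason for new anticancer therapy although SAP 6.2.3 censors for it, so some recorded switchers are reported as ongoing; the SAP 6.2.3 imaging sentence also contradicts Protocol 7.1

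*SAP*

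**What the plan says.** **Censoring rule.** The first censoring bullet in SAP 6.2.3 reads "For participants who start a new anticancer therapy prior to an event, censoring will be at the last adequate tumor assessment" before the new therapy; progression on the same date as the new therapy still counts as an event. Table 2 gives new therapy before progression the outcome *Censored*. SAP 2.1.2 names it as an intercurrent event for both duration endpoints. SAP 5.2.3 derives the start date from three CRF sources and names this censoring as one of its uses. For IC-DoR, SAP 6.2.4 says "Censoring for IC-DoR will be identical to the censoring rules presented above for DoR", with one exception: "Surgery or radiotherapy of extracranial lesions will not affect the determination of IC-DoR".

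**Reporting rule.** SAP 6.2.3 says "Reasons for censoring will be summarized according to the categories in Table 3", with numbers and percentages. Table 3 has four rows:

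1. an event more than 26 weeks after the last adequate assessment;
2. withdrawal of consent;
3. loss to follow-up;
4. *Ongoing without an event*, for which the condition is "No event and none of the conditions in the prior hierarchy are met".

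**Imaging.** SAP 6.2.3 says scans are done at screening and "every 12 weeks until disease progression regardless of initiation of subsequent anticancer therapy". Protocol 7.1 sets scans every 12 weeks, with a one-week window either way: "week till the end of treatment. Tumor assessment should be repeated at the end of treatment if more than 6 weeks have passed", counted from the previous scan.

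**The concern.** The table of censoring reasons is where a reader judges whether censoring is mostly administrative or reflects departures from treatment that may be related to outcome. SAP 6.2.3 itself expects that censoring may be heavy when few responders progress. If a responder who was moved to another therapy is counted as ongoing, the table makes response look better maintained than the data show. No other planned output corrects this: SAP 6.5.5 counts subsequent therapies in the safety set but does not link them to duration-of-response censoring.

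The imaging sentence matters because the SAP uses it to justify the 26-week limit for missing assessments. If scheduled scans stop at end of treatment, a responder who stops without progression has no scheduled scans to miss.

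**Working it through.** **The SAP's own figure.** The gap limit is two 12-week intervals plus two 1-week windows: 2 × 12 + 2 × 1 = 26 weeks. This reproduces the value in SAP 6.2.3 and Tables 2 and 3.

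**Table 3 applied to a recorded switcher.** Take a responder censored under 6.2.3 for a recorded new therapy. Combine three later histories (no progression or death; progression or death 20 weeks after the last adequate assessment; the same at 30 weeks) with three dispositions (neither withdrawn nor lost; consent withdrawn; lost to follow-up). This gives 3 × 3 = 9 paths. The 20-week and 30-week values were chosen to lie on either side of the 26-week limit.

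| After the switch | Neither | Withdrawn | Lost |
|---|---|---|---|
| No progression or death | row 4 | row 2 | row 3 |
| Event at 20 weeks, *No event* read literally | no row | no row | no row |
| Event at 20 weeks, *No event* read as no counted event | row 4 | row 2 | row 3 |
| Event at 30 weeks | row 1 | row 1 | row 1 |

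Under either reading, 0 of 9 paths report the switch as the reason. Row 4 is false for the switchers who reach it. Under the literal reading, progression or death within 26 weeks but after the switch has no category, so the categories would not add up to all censored responders. With a new-therapy row placed first, 9 of 9 paths receive that label.

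**Effect on the estimate.** The censoring date comes from the 6.2.3 text and Table 2. Table 3 only labels observations already censored, so adding a row moves no date and leaves the Kaplan-Meier curve, the median and its interval unchanged.

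**Imaging texts side by side.**

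- SAP 6.2.3: every 12 weeks until progression, including after new therapy starts.
- Protocol 7.1: every 12 weeks until end of treatment, with an end-of-treatment scan if more than 6 weeks have passed.
- Schedule of Activities: no imaging entry in the Follow-Up column. Note 8 and Protocol 6.3 list the follow-up procedures without a scan.
- Outside the schedule, Protocol 7.1 also requires imaging when progression is suspected. Appendix 3 of the protocol, in the context of symptomatic deterioration, asks for efforts to document progression after treatment stops.

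Who is affected by the conflict:

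- Participants treated until progression: the two rules agree.
- Switchers: later data are excluded anyway, so their duration of response is the same under both.
- Responders who stop without progression and without new therapy: the rules differ. The SAP assumes continued scans and the protocol schedules none. Under the protocol schedule they are censored at their last scan unless an event is found within 26 weeks of it. A death later than that is reported in row 1, as an event after missing assessments.

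**The case against.** **The effect is small and confined to a descriptive table.** This stands. Both endpoints are secondary, no test is planned for the primary objective, and no estimate changes.

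**A row may have been lost when the PDF was read.** This is unlikely, because the hierarchy runs from 1 to 4 without a gap.

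**Few switches will be recorded.** Schedule of Activities note 7 and Protocol 5.6 record concomitant therapy only to 28 to 35 days after the last dose, and SAP 6.5.5 uses the short-term follow-up. This limits the count but does not empty the row: SAP 5.2.3 counts any qualifying therapy after the first lorlatinib dose, including curative-intent radiotherapy and resection. Nor does it follow that later switches can never be known. SAP 5.2.3 sets no time limit, and SAP 5.2.4 refers to anticancer therapies given after discontinuation. Late capture is unlikely, not impossible.

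**Stronger readings that a reader might infer, and that the documents do not support:**

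- *All switchers are reported as ongoing.* Those who meet rows 1 to 3 are reported there.
- *Row 4 is false for everyone who has stopped treatment.* The estimand in SAP 2.1.2 runs regardless of time on treatment. For those who stopped without a new therapy the label is imprecise rather than false, and splitting the row would be a matter of preference.
- *The imaging conflict deprives intracranial responders who stop for extracranial progression of their scans.* SAP 6.2.3 also ends imaging at disease progression, and SAP 2.2 ends treatment there. For these participants the two texts agree, and reconciling them would change nothing.

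**Conclusion.** The point holds as a minor internal inconsistency in reporting. Table 3 omits a reason for which the SAP itself censors. By default a recorded switcher is labelled *Ongoing without an event*, and no switcher is reported under the true reason. The wording *No event* also leaves one group without a category if taken literally. The contradiction between SAP 6.2.3 and Protocol 7.1 on imaging is real and separate.

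The documents give neither the number of responders nor the frequency of switching before progression, so the number mislabelled cannot be derived. It is probably small: treatment continues until progression, so many who leave treatment will already have an event, and the recording window is short. A reader might infer that the duration-of-response estimate is biased by the omission. It is not, because the censoring dates are fixed elsewhere, and the primary adverse event endpoint is untouched.

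**What to change.** 1. **Table 3, for duration of response and IC-DoR.**
   - Add a row *Start of new anticancer therapy*, using the SAP 5.2.3 date where it precedes progression or death. Progression on the same date stays an event.
   - State the row's place in the hierarchy.
   - State that *No event* means no counted event, so that every censored responder has exactly one category.
   - For IC-DoR, leave surgery and radiotherapy of extracranial lesions out of the row, in line with SAP 6.2.4.
   - Add a footnote that therapy is systematically recorded only to 28 to 35 days after the last dose.
2. **Imaging.** Reconcile the SAP 6.2.3 sentence with Protocol 7.1 and the Schedule of Activities, including its follow-up notes.

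**Cost.** The Table 3 change is SAP wording and one row. It uses a date already derived, needs no new data and alters no estimate. The same is true of the imaging point if the SAP sentence is aligned to the protocol. Keeping the SAP imaging rule would instead need a protocol change and further scans, and could alter censoring dates and estimates.

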6.2.4. IC-DoR

Analysis set: Subset of Safety Participants with confirmed Intracranial objective response

Analysis methodology: IC-DoR (months) = [first date of PD in brain lesions or death/censoring – first date of IC-OR (CR/PR subsequently confirmed)+1]/30.4375

For participants whose IC-OR proceeds from PR to CR, the onset of PR is taken as the onset of response.

Censoring for IC-DoR will be identical to the censoring rules presented above for DoR.

Intercurrent events and missing data: data on response after subsequent anticancer therapy is administered will be excluded.

Summaries used for reporting: The IC-DoR will be summarized similar to DoR (as described above in section 6.2.3), in Participants with CNS metastases. Surgery or radiotherapy of extracranial lesions will not affect the determination of IC-DoR.

6.3. Other Endpoint(s)

Not applicable.

6.4. Subset Analyses

Not applicable.

6.5. Baseline and Other Summaries and Analyses

6.5.1. Baseline Summaries

• Demographic and Physical Characteristics

The following demographic and baseline characteristics will be summarized by number and percentage:

- o Gender (male, female)
- o Age (18-<45; 45- <65; >65)
- ECOG Performance status

Age (continuous) and weight (kg) will be summarized with descriptive statistics (mean, median, Std Dev, minimum, and maximum, inter quartile range).

Disease Characteristics

The following baseline disease characteristics will be summarized by number and percentage:

Measurable disease at baseline (yes/no) (see Section 5.2.5)
 PFIZER CONFIDENTIAL

^a more than 26 weeks after last adequate tumor assessment.

- o Involved tumor sites at baseline.
- O Number of sites of disease at baseline $(1, 2, \ge 3)$

Involved tumor sites at baseline will be derived from target and non-target lesions at baseline. Each participant will be counted once per organ. Similarly, number of sites of disease at baseline will be derived by counting the number of unique organ sites from target and non-target lesions at baseline. "Other" will be counted as one organ site.

• Medical History

Medical history will be coded using the most current version of MedDRA and summarized by MedDRA's SOC and PT. Each participant will be counted only once within each PT or SOC. Summaries will be ordered by primary SOC and PT in descending order of frequency. Separate summaries will be provided for past and present conditions.

• Prior Anticancer Treatments

Prior anticancer treatments include systemic therapy, radiation, and surgery. The number and percentage of participants in each of the following anticancer therapy categories will be tabulated:

- o Participants with at least one type of prior anticancer treatment;
- o Participants with at least one prior anticancer drug therapy;
- o Participants with at least one prior anticancer radiotherapy;
- o Participants with at least one prior anticancer surgery.

Prior anticancer drug therapy will be summarized as follows based on the number and percentage of participants:

- o Number of prior anticancer therapy regimens: missing $/1/2/3/\ge 4$;
- o Number of participants who received prior chemotherapy
- Number of participants who received 1st generation (Crizotinib) or 2nd generation (Alectinib, Certinib or Brigatinib) ALK Inhibitor (ALKi) as Prior ALKi

The prior anticancer drugs will be coded in the World Health Organization (WHO) Drug coding dictionary.

6.5.2. Study Conduct and Participant Disposition

6.5.2.1. Disposition

A summary of the number of participants enrolled by site will be provided for the Enrolled analysis set.

Discontinuations from study will be summarized using the Enrolled set. Discontinuations from study treatment will be summarized using the Safety analysis set.

Discontinuations from study treatment due to adverse events will be identified as either related or not related to study treatment. If causality is missing, the event will be considered related to treatment. If multiple events lead to study treatment discontinuation and at least one was considered related, discontinuation will be reported as related to study treatment.

6.5.2.2. Protocol Deviations

Protocol deviations will be compiled prior to database closure and will be summarized by category (n(%)) for the Enrolled Analysis Set. Categories will be assigned by the study Clinician.

6.5.3. Study Treatment Exposure

6.5.3.1. Exposure to lorlatinib

Exposure will be summarized for the Safety analysis set.

The summary of treatment exposure for lorlatinib will include the following information:

- Treatment duration (days)
- Cumulative dose (mg)
- Dose intensity (mg/day)
- Relative dose intensity (%).

The duration of lorlatinib (in days) is defined as:

```
Treatment duration (days) = (last dose date - first dose date + 1)
```

The cumulative dose (mg) of lorlatinib is the sum of the actual dose levels that the participant received (i.e., total dose administered (mg)).

The dose intensity (DI) and the relative dose intensity (RDI) of lorlatinib will be calculated for each participant during the study. The DI (mg/day) of lorlatinib during the study is defined as

```
DI(mg/day) = [cumulative dose(mg)]/[treatment duration(days)]
```

The RDI of lorlatinib is defined as the ratio of the DI and planned dose intensity d and expressed in %

RDI (%) =
$$100 \times [DI (mg/day)/[d (mg/day)].$$

6.5.3.2. Dose Reductions and Interruptions

A dose reduction is defined as a non-zero dose that is less than the prior dose.

The number and percentage of participants with at least one dose reduction as well as a breakdown of dose reductions $(1/2/3/\ge4)$ will be summarized.

Reasons for dose reductions will also be summarized. Participants can contribute to more than one reason if multiple dose reductions occurred for different reasons but will only be counted once per reason. Percentages will be calculated based on the total number of participants in safety analysis set.

An interruption is defined as a 0 mg dose administered on one or more days. (Note: A dose interruption is not considered a dose reduction). The number and percentage of participants with dose interruptions and the corresponding reasons will be summarized. Participants can contribute to more than one reason if multiple dose interruptions occurred for different reasons but will only be counted once per reason. Percentages will be calculated based on the total number of participants in safety analysis set.

The following define how dose interruptions will be counted in the case of multiple dose interruptions:

- If an interruption occurs consecutively for at least two days due to the same reason, then it will be counted only once.
- If an interruption occurs consecutively for at least two days due to different reasons, then it will be counted for each reason.
- If an interruption occurs for more than one day due to the same reason, but the days are not consecutive, i.e. there is at least one dosing day in between, then each dose interruption will be counted as a different occurrence.

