## 5.3. Administration

The product will be administered in accordance with the label.

The recommended dosage of lorlatinib is 100 mg orally QD, with or without food, until disease progression, unacceptable toxicity, or participant refusal/lost to follow-up. Tablets should be swallowed whole. Tablets should not be chewed, crushed, or split. Tablets should not be taken if they are broken, cracked, or otherwise not intact. Lorlatinib should be taken at the same time each day. If a dose is missed, then the missed dose should be taken unless the next dose is due within 4 hours. Two (2) doses should not be taken at the same time to make up for a missed dose. An additional dose should not be taken if vomiting occurs after lorlatinib but the next scheduled dose should be continued. Dosing interruption or dose reduction may be required based on individual safety and tolerability.

Lorlatinib dose reduction levels are summarized below:

- First dose reduction: 75 mg taken orally QD;
- Second dose reduction: 50 mg taken orally QD.

Lorlatinib should be permanently discontinued if the participant is unable to tolerate the 50 mg dose taken orally QD. Dose modification recommendations for adverse reactions are provided in Table 2.

Adverse Reaction	Lorlatinib Dosing
CNS Effect	
Grade 1	Continue lorlatinib at same dose or withhold the
	dose until recovery to baseline. Resume lorlatinib at
	the same dose or at a reduced dose.
Grade 2 or Grade 3	Withhold dose until Grade 0 or 1. Resume lorlatinib
	at a reduced dose.
Grade 4	Permanently discontinue lorlatinib.
Hyperlipidemia	
Grade 4 hypercholesterolemia or Grade 4	Withhold lorlatinib until recovery of
hypertriglyceridemia	hypercholesterolemia and/or hypertriglyceridemia to
	less than or equal to Grade 2. Resume lorlatinib at
	the same dose. If severe hypercholesterolemia
	and/or hypertriglyceridemia recurs, resume lorlatinit
	at a reduced dose.
AV block	
Second-degree AV block	Withhold lorlatinib until PR interval is less than
	200 msec. Resume lorlatinib at a reduced dose.
First occurrence of complete AV block	Withhold lorlatinib until:
	
 
pacemaker placed, or
 

	• PR interval less than 200 msec.
	If a pacemaker is placed, resume lorlatinib at the
	same dose. If no pacemaker is placed, resume
	lorlatinib at a reduced dose.
Recurrent complete AV block	Place pacemaker or permanently discontinue
	lorlatinib.
ILD/Pneumonitis	
Any grade treatment-related ILD/Pneumonitis	Permanently discontinue lorlatinib.

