Other adverse reactions	
Grade 1 or Grade 2	Continue lorlatinib at same dose or reduced dose.
Grade 3 or Grade 4	Withhold lorlatinib until symptoms resolve to less
	than or equal to Grade 2 or baseline. Resume
	lorlatinib at reduced dose.

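### Read literally, the SAP's dose-reduction rule does not count a lower dose resumed straight after a 0 mg hold, because it does not restrict the prior dose to non-zero doses

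*SAP*

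**What the plan says.** SAP 6.5.3.2 gives two definitions. For reductions: "A dose reduction is defined as a non-zero dose that is less than the prior dose". For interruptions: "An interruption is defined as a 0 mg dose administered on one or more days". A note adds that an interruption is not itself a reduction. The first definition feeds "The number and percentage of participants with at least one dose reduction as well as a breakdown of dose reductions" into 1, 2, 3 and 4 or more, together with a summary of reasons. Protocol 9.6 (Study Treatment Exposure) commits to reporting reductions and their reasons.

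Protocol 5.3 names the lower dose levels as reductions, for example "First dose reduction: 75 mg taken orally QD", with 50 mg as the second. Its Table 2 reaches a lower dose in several ways:

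- **Hold stated.** For second-degree AV block, lorlatinib is withheld and then: "Resume lorlatinib at a reduced dose". CNS effects of Grade 2 or 3, and a first complete AV block without a pacemaker, follow the same pattern. So do other Grade 3 or 4 reactions, whose entry begins "Withhold lorlatinib until symptoms resolve to less".
- **Hold implied.** For recurrent severe lipid abnormalities the entry reads "and/or hypertriglyceridemia recurs, resume", again at a reduced dose.
- **Hold optional.** For CNS Grade 1, after the optional hold, treatment resumes at "the same dose or at a reduced dose".
- **No hold stated.** Other Grade 1 or 2 reactions may go straight to a lower dose.

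Outside Table 2, Protocol 5.6.1 describes a lower dose when a strong CYP3A inhibitor is co-administered, also with no hold stated.

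**The concern.** The reduction rule requires the current dose to be non-zero but places no such condition on the dose it is compared with. Since the next definition treats a hold as a dose of 0 mg, the dose immediately before a resumption can be 0 mg. No positive dose is below 0, so a resumption at a lower level directly after such a record can never qualify.

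The stake is a tolerability summary that the Protocol promises. A participant whose only reduction followed a hold would drop out of the count of participants with at least one reduction. A participant with one direct and one post-hold reduction would be placed in the wrong breakdown category. The reasons attached to the missed reductions would drop out too. The error would run in one direction, towards fewer reductions.

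**Working it through.** The documents state no expected number of reductions, so there is no planned figure to reproduce. The check applies the definition to example sequences built from the Protocol 5.3 dose levels (100, 75 and 50 mg) and 0 mg for a hold.

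**Rules compared.** Let d(i) be the i-th dose record.

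- Literal: record i is a reduction if d(i) > 0 and d(i) < d(i−1).
- Last non-zero: record i is a reduction if d(i) > 0 and d(i) is less than the most recent non-zero dose before it.

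**One sequence in full, 100-0-75.** The second record is 0, so it fails the non-zero condition under both rules. For the third, the literal rule asks whether 75 < 0, which is false; total 0. The last-non-zero rule asks whether 75 < 100, which is true; total 1.

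**Results**

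| Sequence (mg) | Literal | Last non-zero | Effect of the literal rule |
|---|---|---|---|
| 100-0-75 | 0 | 1 | participant lost from the count |
| 100-0-75-0-50 | 0 | 2 | participant lost from the count |
| 100-75-0-50 | 1 | 2 | wrong breakdown category |
| 100-75 | 1 | 1 | none |
| 100-75-50 | 2 | 2 | none |
| 100-0-100 | 0 | 0 | none |

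**Holds stored as gaps.** With the 0 mg records removed, the first three sequences become 100-75, 100-75-50 and 100-75-50. The literal rule then gives 1, 2 and 2, the same as the last-non-zero rule. The miscount therefore needs 0 mg records in the series.

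**Direct step-downs.** A reduction made on treatment with no hold, whether for another Grade 1 or 2 reaction or for a strong CYP3A inhibitor (75-50, for instance), is counted under either rule.

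**Other exposure measures.** SAP 6.5.3.1 computes cumulative dose and dose intensity without the reduction rule. For an illustrative 10 days at 100 mg, 7 days at 0 and 20 days at 75 mg, cumulative dose is 1000 + 0 + 1500 = 2500 mg over 37 days. Dose intensity is 2500/37 = 67.57 mg/day however reductions are counted. Relative dose intensity is a multiple of that figure. Interruptions have their own counting rules in 6.5.3.2, which do not refer to the prior dose.

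**The case against.** The strongest reply is that no sensible programmer would treat a day without drug as the prior dose. There is support for this. SAP 3.4 defines first and last dose by non-zero dosing. SAP 5.2.2 starts a cycle at a dose above zero. The interruption rules in 6.5.3.2 contrast hold days with a dosing day. The intended comparison was probably with the last dose taken. The exposure CRF layout is also not in the documents, so 0 mg storage cannot be confirmed.

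This limits the point but does not remove it. The non-zero qualifier on the current dose would be unnecessary if 0 mg entries could not appear in the series. Where the SAP wants zeros skipped elsewhere it says so, and here it does not. Two programmers could follow the text faithfully and produce different tables.

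A reader might go further and infer that most reductions will be missed, because most Table 2 routes to a lower dose involve a hold. The documents do not support that. Table rows are not participants, some of the holds are implied or optional, and Protocol 5.6.1 adds reductions with no hold stated.

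Nor would a mismatch with the adverse event tables prove a miscount. Under SAP 6.1.1.1 those tables use the investigator's entry for action taken on the adverse event form and cover only reductions associated with an event. A reduction made for co-medication could separate the two tables even when both are counted correctly.

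**Conclusion.** The rule is wrong as written, and the consequence is minor. The miscount requires two conditions: holds are stored as 0 mg records, and the rule is programmed literally. If both hold, each lower dose resumed directly after a hold is missed. If either fails, the counts are right. The documents settle neither, so this is a defect of wording and not a demonstrated miscount. The number of participants affected cannot be derived.

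The effect is confined to the reduction part of the exposure summary in SAP 6.5.3.2. It would be wrong to infer that the primary safety analysis is compromised. Adverse event incidence and event-associated reductions do not use the rule, and neither do interruption counts, cumulative dose, dose intensity or relative dose intensity. SAP 5.1 plans no hypothesis test and no decision rule for the primary objective.

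**What to change.** In SAP 6.5.3.2, change the comparator so that a reduction is a non-zero dose below the last preceding non-zero dose, ignoring any intervening 0 mg records.

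Leave the interruption rules as they stand. It is tempting to add that a hold followed by a lower dose counts as one interruption and one reduction. That would conflict with the same section, which counts a continuous hold with different reasons once for each reason.

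The cost is one phrase in the SAP and a short programming check before database release, for which the sequences in the table above are enough. If holds turn out to be stored as gaps, the new wording gives the same counts as the present one. This is a counting rule only and changes no dosing.
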